Don't Throw Your Heart Away: Clinician Study 3 Protocol

NCT04455893

Last IRB Check-In: Jan 10 2024

Study Information

Hypotheses

Hypothesis 1 When transplant centers present information on their transplant success rate only, evaluators will respond by selecting hospitals with higher transplant success. However, if information presented on transplant outcomes is stratified by the number and quality of donors used, or displayed in addition to total survival rates, then participants will respond by selecting hospitals with higher organ acceptance rates rather than the hospital with higher transplant outcomes. Thus, preference for the non-selective transplant center (relative to the selective center) will be lower in condition 1 (baseline: combined transplant survival only), compared to condition 2. That is, a higher proportion of participants will prefer the non-selective center over the selective center in condition 2, relative to condition 1. Hypothesis 2 The effect of information condition on choice will be mediated by ratings of the importance of getting a heart at all. That is, viewing information about stratified transplant survival will lead participants to think that the chance to "get a heart at all" is a more important factor in their decision which will in turn be associated with higher preference for the non-selective hospital. Specifically, ratings of importance (0-100 continuous scale) for the item "likelihood of getting any heart" will be lower in condition 1 than in condition 2. Furthermore, ratings on this item will be associated with choice, such that higher ratings will be associated with choice of the non-selective center. A bootstrapped mediation analysis will test for an indirect effect. Hypothesis 3 The difference in hospital preference between the treatment (stratified transplant survival) and control (combined transplant survival) conditions for the clinician participants will be smaller than the analogous difference observed in a previous study of layperson (Amazon Mechanical Turk) participants exposed to the same two conditions. In an analysis combining the data from the current study and the layperson study from the same two conditions in the previous study, we predict a 2 (information condition) x 2 (participant population) interaction, such that that effect of information condition is smaller for expert clinicians than for lay people.

Design Plan

Study type

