Experiment - A researcher randomly assigns treatments to study subjects, this includes field or lab experiments. This is also known as an intervention experiment and includes randomized controlled trials.

Blinding

- For studies that involve human subjects, they will not know the treatment group to which they have been assigned.

Is there any additional blinding in this study?

n/a

Study design

We have a between-subjects design in which participants are randomized to one of two information conditions (independent variable). In each condition, they make a choice (dependent variable) between two hospitals (one with a non-selective donor acceptance strategy, and another with a more selective donor acceptance strategy). Independent variables: (1) Condition 1 ("baseline" condition): view only combined transplant survival (e.g. transplant

survival rate not stratified by number and quality of donor hearts accepted at each center) (2) Condition 2: view only stratified transplant survival (e.g. transplant survival rate stratified into patients who received excellent donor organs and patients who received less than optimal donor organs) These two conditions will be analyzed for our primary analysis: a 1x2 design with 2 arms (control arm or combined transplant survival, and experimental arm or stratified transplant survival).

Randomization

We will use simple randomization, where each participant will be randomly assigned to one of the two predetermined conditions. The Qualtrics randomizer function will be used for randomization into a condition.

Sampling Plan

Existing Data

Registration prior to creation of data

Explanation of existing data

n/a

Data collection procedures

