The outcome variable will be a binary choice between two hospitals: one with a selective donor-heart acceptance strategy and one with a non-selective donor heart acceptance strategy. Participants will respond to the question "Which Hospital do you consider to be higher performing? Please click on one of the two tables below to indicate which hospital is the better choice." Participants will choose between two outcome tables featuring the selective and non-selective hospital (counterbalanced, such that each of the two choices is equally likely to be presented at top of the choice scenario in each condition). The number of participants that choose each hospital will be the measured outcome variable used in analyses. On the next page of the survey, participants will respond to three mediator questions: "There are many reasons why one transplant hospital might outperform another. Which reasons were most important in your decision? Please move the slider to indicate how much you considered each of the reasons below (0=reason was not important, 100=reason was extremely important)." Participants will then move a slider bar (0-100) to indicate the importance of the following three items: (1) Patients were more likely to receive an excellent donor heart at the hospital I picked. (2) Patients were less likely to receive a marginal donor heart at the hospital I picked. (3) Patients were more likely to receive any kind of heart at the hospital I picked. The third item (more likely to receive any kind of heart) will be the only variable that is included in the planned mediation analysis.

Indices

n//a

No files selected

Analysis Plan

Statistical models

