To test Hypotheses 1, we will use a binomial logistic regression analysis. The categorical independent variable will be 'stratified transplant survival'; the dependent variable is binary choice of hospital. -We will test whether the main effect of "stratified transplant survival" is statistically significant and in the predicted positive direction. To test Hypothesis 2, we will conduct a causal mediation analysis to determine whether information display had a mechanistic effect on hospital choice through our proposed mediator. We will estimate the average causal mediation effect (ACME), average direct effect (ADE), and the total effect. The ACME is the effect of the experimental information display condition (stratified) on the outcome of hospital choice (selective vs. non-selective), mediated through the hypothesized mediator (the importance of "getting any heart" at each hospital when considering the choice). The remaining effect of information display on hospital choice that is not mediated through the hypothesized mediator represents the ADE. The entire effect of the information display on hospital choice via the hypothesized mediator and the direct effect is the total effect. The proportion of the total effect that is accounted for by the ACME is called the proportion mediated.{Imai, 2010}. Analyses will be performed using the "mediation" package in R (The R Foundation for Statistical Computing).{Tingley, 2014}. We will generate 95% confidence intervals by using 1000 bootstrap simulations. The unstandardized point estimate of the ACME and its 95% confidence intervals will be interpreted. -A significant ACME for "stratified transplant survival" would suggest that stratifying transplant survival by number and quality of accepted donors works via increasing the perceived importance of "getting any heart" to increase preference for the non-selective hospital. If the ACME is non-significant, we will identify where the causal path breaks down. To test Hypothesis 3, we will conduct an analysis combining the data from the current study and the layperson study from the same two conditions in the previous study. We predict a 2 (information condition) x 2 (participant population) interaction, such that that effect of information condition is smaller for expert clinicians than for laypeople.

No files selected

Transformations

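### The sole Hypothesis 2 mediator is rated after the hospital choice and worded about the hospital picked, so the planned ACME rules cannot tell mediation from post-choice justification

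*Combined protocol and SAP*

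**What the plan says.** Under Variables, Measured variables, the participant first clicks on one of two hospital tables, and that click is the outcome. Then: "On the next page of the survey, participants will respond to three mediator questions". The stem asks for "how much you considered each of the reasons below", on a 0–100 slider. Item 3 reads "Patients were more likely to receive any kind of heart at the hospital I picked", and it alone enters the mediation analysis.

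Hypothesis 2 orders the steps differently. The display raises the importance of getting a heart at all, "which will in turn be associated with higher preference for the non-selective hospital". It labels the item "likelihood of getting any heart" and predicts that its ratings "will be lower in condition 1 than in condition 2".

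Analysis Plan, Statistical models, sets up a causal mediation analysis "to determine whether information display had a mechanistic effect on hospital choice through our proposed mediator". It estimates the ACME, direct effect, total effect and proportion mediated, with 95% intervals from 1000 bootstrap simulations. A significant ACME is to be taken as suggesting that stratification operates through this reason. A non-significant one is to be followed by a search for the link at which the causal chain fails. The mediator is described there as importance at each hospital at the time of choosing.

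On allocation, Design Plan, Randomization, says "each participant will be randomly assigned to one of the two predetermined conditions". The plan has no rating before the choice, no randomized order of choice and rating, no manipulation of the mediator, and no caveat about order. The counterbalancing concerns only which hospital table appears on top.

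**The concern.** A mediator has to act before the outcome. Here the outcome is recorded first, and the hospital that item 3 refers to is set by the answer just given: people who chose differently rate statements about different hospitals. The rating may report reasoning that led to the choice, or it may be shaped by the choice, or both. If it is shaped by the choice, a display that changes choices will also change ratings, and the mediation model will attribute part of the effect on choice to the rating.

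At stake is the causal reading of one of three pre-specified hypotheses. A significant ACME could be reported as a mechanism when there is none. A null ACME could be read as a broken causal link when mediation is present but masked.

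**Working it through.** **1. The plan's own figure.** The only sample-size figure is for Hypothesis 1: 61 per group, at least 90% power, 35% vs 65%, α = 0.05. Exact power of the two-sided Fisher test is 90.07% at 61 per group and 89.24% at 60, so 61 is reproduced. There is no figure for Hypothesis 2.

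**2. What the design identifies.** Let T be condition, M the rating and Y the choice. Because T is randomized, its effects on Y and on M as measured are identified. Data generated purely by justification have the distribution P(T)·P(Y|T)·P(M|T,Y). The same distribution can always be written P(T)·P(M|T)·P(Y|T,M), which is the form the mediation model fits. The data cannot choose between the two. A standard ACME sensitivity analysis for unmeasured confounding would not help, since it also takes M to precede Y.

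**3. Illustration with zero mediation.** From the documents: 61 per arm, 35% vs 65%, 0–100 scale, 1000 bootstrap draws. Assumed: M is normal with SD 25, mean 50 − gap/2 for selective choosers and 50 + gap/2 for non-selective choosers, clipped to 0–100. Y depends on T only. Analysis: linear M on T, logistic Y on T and M, ACME averaged over both conditions, significant if the percentile 95% CI excludes 0. There were 1000 trials per row, with Monte Carlo SE at most √(0.5 × 0.5/1000) = 0.016. The mean total effect was 0.301.

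| Gap (points) | ACME significant | Mean ACME | Apparent share mediated |
|---|---|---|---|
| 0 | 0.4% | 0.000 | 0% |
| 10 | 4% | 0.010 | 3% |
| 20 | 23% | 0.037 | 0.037/0.301 = 12% |
| 35 | 51% | 0.092 | 0.092/0.301 = 31% |
| 50 | 71% | 0.142 | 0.142/0.301 = 47% |

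Why it happens: the arms differ in rating by (0.65 − 0.35) × gap, that is 0.30 × 20 = 6.0 or 0.30 × 35 = 10.5 points before clipping (5.6 and 9.7 after). This is a real effect on the rating as measured, but it arises only through the choice.

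**4. Range at gaps of 20 and 35 points, zero mediation.**
- 40% vs 60%: 13% and 26%. 42.5% vs 57.5%: 8% and 16%.
- No effect of condition on choice (50% vs 50%): 4% and 4%.
- SD 20: 33% and 62%. SD 30: 16% and 41%.
- 50 per arm (the 100-response stopping rule): 17% and 42%.
- Ratings follow choice in the stratified arm only: 4% and 14% with control ratings at 50; 38% and 92% in the special case of control ratings at the selective choosers' mean.

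**5. Reversed gap.** At −20 points, with selective choosers rating higher, the spurious ACME is still positive: mean 0.038, significant in 26% of 200 trials (300 draws each). Both the condition-to-rating and the rating-to-choice coefficients change sign, so their product does not.

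**6. Real mediation plus justification.** Assumed: pre-choice importance L has mean 45 or 55 by arm, SD 25, clipped; the log-odds of the non-selective choice rise 0.5 per 25 points of L; arm intercepts are set to give 35% and 65%. The reported rating is L + g(Y − 0.5), clipped. The true ACME is 0.043, or 0.043/0.30 = 14%.

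| Post-choice shift g | Mean ACME | Share mediated |
|---|---|---|
| −20 | −0.010 | −0.010/0.30 = −3% |
| −10 | 0.003 | 0.003/0.30 = 1% |
| 0 | 0.041 | 14% |
| +10 | 0.091 | 31% |
| +20 | 0.141 | 48% |
| +35 | 0.198 | 68% |

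The negative rows use 200 trials of 300 draws, the others 1000 of 1000. Relative to the estimate without a shift, inflation is 0.307/0.137 = 2.2, 0.476/0.137 = 3.5 and 0.678/0.137 = 4.9. With a true share of 50% it could not exceed 1/0.5 = 2 while the estimate stays at or below 100%.

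**The case against.** Several counter-arguments have weight.

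- **The wording is hedged and Hypothesis 2 is not primary.** Both are true, and they limit the weight of the point. But the stated aim of the analysis is to determine a mechanism, and the hedge says nothing about order.
- **The stem asks about reasoning during the decision.** It does, so genuine mediation is possible. Recall after the choice still does not fix direction.
- **The sizes are assumed.** They are: the documents give no SD, chooser gap or strength of justification, and the results run from 0.4% to 92%. The argument in step 2 needs none of them.
- **The labels in Hypothesis 2 and Statistical models are shorthand for item 3.** This is fair. Measured variables leaves no doubt which item is used, so the mismatch is minor and calls only for alignment.
- **Choice first is sensible.** Agreed. Asking the item earlier could prime the Hypothesis 1 outcome.

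A reader might go further and infer that the bias always favours mediation, or that the share mediated is inflated several-fold. The documents support neither. Someone who picked the selective hospital could also rate item 3 up in justification, which can hide real mediation (step 6, negative shifts). Several-fold inflation needs a small true share and a shift of about 20 points or more.

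**Conclusion.** The point holds as a limit on interpretation and should be fixed. The direction between rating and choice is not identified, so neither the rule for a significant ACME nor the rule for a null one is supported. Under the assumed inputs, and with ratings following choice in both arms at the powered effect, the false-signal rate is material from gaps of about 20 points (23%, and about 50% at 35). It is near nominal at gaps of 10 or less, or when condition does not affect choice. Where some mediation is real, the bias can run either way.

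A reader might also infer that mediation is absent, or that the rating data are worthless. Neither follows: the condition difference in the rating is a valid randomized comparison of the rating as measured. Hypothesis 1, the Hypothesis 3 choice comparison and the sample size do not use the rating and are untouched.

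**What to change.** Keep the choice first. In Statistical models, and to match in Hypothesis 2, state that:

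- (a) the condition difference in the item 3 rating is a randomized comparison, reported with a 95% CI as the effect of the display on the rating as measured;
- (b) the relation between rating and choice within condition is reported with a 95% CI as an association;
- (c) because the rating follows the choice, the ACME and proportion mediated are model-based quantities consistent with, but not evidence for, mediation over post-choice justification; they may be biased in either direction and will not support a conclusion about mechanism;
- (d) if the ACME is non-significant, (a) and (b) are reported separately, (b) is not read as a directional causal step, and absence of mediation is not concluded.

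Describe the mediator in both sections as item 3 is actually asked.

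The cost is a weaker Hypothesis 2 claim and two extra reported intervals, with no new data. If data are already collected, record this as a dated change to the registered plan.

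### A significant indirect effect in Hypothesis 2 is read as a causal mechanism, but the rating-to-choice path is not randomised, no covariate is listed and no sensitivity analysis is planned

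*Combined protocol and SAP*

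**What the plan says.** All references are to the combined protocol and SAP.

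- **Analysis Plan, Statistical models.** For Hypothesis 2, "we will conduct a causal mediation analysis to determine whether information display had a mechanistic effect on hospital choice through our proposed mediator". The ACME, the average direct effect, the total effect and the proportion mediated are to be estimated in R. On uncertainty: "We will generate 95% confidence intervals by using 1000 bootstrap simulations". A significant ACME is taken to suggest that the stratified display "works via increasing the perceived importance of 'getting any heart' to increase preference for the non-selective hospital". The only follow-up described is for a non-significant ACME.
- **Design Plan, Randomization.** The object of randomisation is the display: "each participant will be randomly assigned to one of the two predetermined conditions".
- **Variables, Measured variables.** The listed measures are the binary choice and three importance sliders. "The third item (more likely to receive any kind of heart) will be the only variable that is included in the planned mediation analysis". On timing, after the choice has been made: "On the next page of the survey, participants will respond to three mediator questions". Each slider is worded in terms of the hospital the respondent has picked.
- **Not found.** No baseline characteristic or prior view is listed as measured or adjusted for. The assumption that rating and choice share no unmeasured cause is not stated. No sensitivity analysis is given, and the Exploratory analysis field has no response.

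**The concern.** Randomisation protects the effect of display on rating and the total effect of display on choice. It does not protect the effect of rating on choice, which is the other half of the ACME. That half is causal only if, within each arm, nothing unmeasured drives both rating and choice (part of the assumption called sequential ignorability).

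The respondents are transplant clinical personnel, who are likely to hold prior views on donor acceptance. One who favours wider use of donor hearts would tend both to rate getting any heart as important and to pick the non-selective hospital, whichever display was shown. If the display also raises the rating, the product of the two paths is positive even when the rating does nothing. The bootstrap interval measures sampling error and does not reflect this bias.

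At stake is the mechanism conclusion of one of three registered hypotheses.

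**Working it through.** **1. The plan's own figure.** Sample size rationale: 61 per group, 35% vs 65%, alpha 0.05, at least 90% power. Exact two-sided Fisher power at 61 per arm is 0.9007, so the figure reproduces. The plan states no power or error rate for Hypothesis 2.

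**2. Model with no rating effect on choice.** Inputs from the plan: 61 per arm, choice 35% vs 65%, 1000 bootstrap draws. Assumed: *a*, the display's effect on the rating in SD units, and *rho*, the within-arm correlation of rating and latent-choice errors.

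- Rating: M = a·T + √rho·U + √(1−rho)·e1
- Choice: Y = 1 if μ_T + √rho·U + √(1−rho)·e2 > 0, with μ_0 = Φ⁻¹(0.35) = −0.385 and μ_1 = Φ⁻¹(0.65) = +0.385

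U is the unmeasured attitude. M does not appear in the equation for Y, so the true ACME is 0.

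**3. Size of the spurious ACME.** Within arm, the regression of the latent choice on M has slope rho, so moving the rating by *a* appears to move the latent mean by rho·a. The spurious ACME is Φ(μ_0 + rho·a) − 0.35, and by symmetry it is the same in the other arm.

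- a = 0.3, rho = 0.2: Φ(−0.325) − 0.35 = 0.3725 − 0.35 = 0.022
- a = 0.5, rho = 0.2: Φ(−0.285) − 0.35 = 0.3877 − 0.35 = 0.038
- a = 0.5, rho = 0.3: Φ(−0.235) − 0.35 = 0.4070 − 0.35 = 0.057

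The simulated means are 0.023, 0.036 and 0.057. Against a total effect of 0.30, the last two of the closed-form values are spurious proportions mediated of 13% and 19%.

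**4. How often it is significant.** 300 simulated trials per setting; linear model for the rating; logistic model for choice on display and rating (the plan does not name the link for the mediation outcome model); ACME averaged over arms; percentile 95% interval. The table gives the share of trials with the interval wholly above 0 (nominal 2.5%):

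| Shift a | rho 0 | 0.1 | 0.2 | 0.3 | 0.5 |
|---|---|---|---|---|---|
| 0 | 0% | 0% | 1.3% | 2.3% | 3.3% |
| 0.3 SD | 0.3% | 2.7% | 13% | 27% | 38% |
| 0.5 SD | 4.0% | 11% | 31% | 53% | 76% |
| 0.8 SD | 4.3% | 13% | 43% | 75% | 99% |

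The Monte Carlo standard error is about 1 to 3 points: √(0.133 × 0.867/300) = 2.0 points and √(0.533 × 0.467/300) = 2.9 points. Repeat runs at a = 0.3 gave 13-18% (rho 0.2) and 25-27% (rho 0.3). At a = 0.5 they gave 29-36% and 52-63%. With no shift, the highest rate in any run was about 5%. Clipping the rating to a 0-100 slider at a = 0.3 gave 13% and 25%. The excess appears only when both *a* and *rho* are above zero.

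**5. The reverse route.** In a further simulation the rating again had no effect on choice, but choice raised the rating by *c* SD and the display raised it directly by *a* SD (both assumed; 250 datasets, 250 bootstraps, probit outcome model). Suppose causal wording were allowed whenever the ACME interval excluded 0 at every rho up to 0.3. For c = 0.5, 0.8, 1.0 and 1.5, that rule would be passed in 1%, 29%, 61% and 93% of trials at a = 0.3, and in 2%, 37%, 71% and 98% at a = 0.5.

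**The case against.** **The rates rest on assumptions.** This stands. A reader might infer that the false-positive rate for the mechanism claim simply is far above 5%. The documents do not support that. They give neither the rating shift nor the error correlation, and the rate stays low if either is small: 2.7% at a = 0.3 with rho = 0.1, and about 5% or less with no shift. The condition on the shift is nevertheless the one that Hypothesis 2 itself predicts.

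**The absence of covariates is inferred from silence.** This stands in part. The sentence saying that the third item "will be the only variable that is included in the planned mediation analysis" picks one slider out of three. It cannot be read literally, since display and choice are also in the analysis, and it does not forbid covariates. The supportable statement is that none is listed; the full questionnaire is not in the documents.

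**The wording is hedged and the scope is limited.** The plan says a significant ACME would suggest the pathway, and Hypothesis 2 is not the primary analysis. Both are true. The stated purpose is still to determine a mechanistic effect, and nothing in the plan tests a significant result.

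**A sensitivity analysis could earn the causal claim.** A reader might infer that surviving up to some chosen rho, such as 0.3, would justify it. It would not. No cutoff has a basis in the documents, and that analysis takes the rating to precede choice, whereas the survey collects it afterwards (step 5). A cutoff would also be costly. With genuine mediation, no confounding and a = 0.5, the planned test detects the effect in 56% of trials (probit slope 0.3 per SD) or 80% (slope 0.5), but a 0.3 cutoff would pass only 4% or 27%.

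**Conclusion.** The concern holds in conditional form. Followed as written, the plan can report a mechanism where the rating has no effect on choice. For rating shifts of 0.3-0.5 SD, the rate of a significant positive ACME is roughly 13-31% at an error correlation of 0.2, 27-53% at 0.3 and 3-11% at 0.1, against a nominal 2.5%. This requires both that the display shifts the rating and that unmeasured attitudes link rating to choice. The sizes are illustrative, since both quantities are assumed.

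Collecting the rating after the choice is a separate weakness. Baseline covariates would not remove it and the rho analysis does not rule it out. The randomised comparison for Hypothesis 1 is unaffected.

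**What to change.** In the Hypothesis 2 text of Statistical models:

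1. State that a causal reading of the ACME assumes no unmeasured common cause of rating and choice within arm, and that the rating is not randomised.
2. Fit the mediation outcome model as a probit, run the mediation package's sensitivity analysis, and report the ACME across rho and the rho at which it becomes zero.
3. Replace the mechanism reading with associational wording, for example: *a significant ACME is consistent with the proposed pathway; because the rating is observational and is collected after the choice, it does not establish that pathway.* Use this wording whatever the sensitivity analysis shows, and set no rho cutoff that would permit a causal claim.

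Recording professional role and society at the end of the survey is optional. They would capture prior attitude only in part and do not replace the steps above.

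The cost is one further analysis in the R package already named, a few sentences, and a more cautious conclusion for Hypothesis 2. The three steps need no new data.

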125 transplant clinical personnel participants will be recruited from the International Society for Heart and Lung Transplantation (ISHLT) and the Pediatric Heart Transplant Society (PHTS). Participants will be recruited via (1) the ISHLTConnect Discussion Board webpage, (2) the PHTS Basecamp Discussion Board webpage and corresponding Listserv, and (3) the PHTS July 2020 Live Webinar (via Zoom). Inclusion criteria: Participants who are transplant clinical personnel will be asked to participate if they confirm the following inclusion criteria in the consent form. (1) 18 years of age or older (2) must read and understand the information in the consent form (3) must want to participate in the research and continue with the survey Payment: Participants will be given the option to select a transplant-related charity at the end of the survey that will receive a \$1.50 donation (anonymously) if they complete the survey.

Sample size

Our target sample size is 122 participants. We expect that this will amount to approximately 61 participants per condition, although due to the nature of the randomization technique used (Qualtrics randomizer function), we may end up with slightly more or slightly less than 61 per condition.

Sample size rationale

A sample size of 61 per group was calculated to yield at least 90% power to detect a 30 percentage point difference between conditions (e.g., 35% vs. 65%) with $\alpha=0.05$ (GPower 3.1.9.4).

Stopping rule

We will stop data collection after the first of the following three scenarios is achieved: (1) 122 responses collected (2) August 31, 2020 and at least 100 responses collected (3) October 31, 2020.

Variables

Manipulated variables

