Logistic regression analysis: The categorical predictor "transplant survival stratified" will be dummy coded (0=not stratified, 1=stratified), with 'stratified' as the reference category. The outcome variable "choice of hospital" will be dummy-coded (0=selective hospital, 1=non-selective hospital). The reference category is 'selective hospital'. Mediation analysis: The categorical predictor "transplant survival stratified" will be dummy coded (0=not stratified, 1=stratified), with 'stratified' as the reference category. The continuous mediator variable "get any heart" will be mean-centered for each analysis. The outcome variable "choice of hospital" will be dummy-coded (0=selective hospital, 1=non-selective hospital). The reference category is 'selective hospital'.

Inference criteria

We will use the standard $p=0.05$ criteria for determining if the results are significantly different from those expected if the null hypothesis were correct.

Data exclusion

n/a

Missing data

If a participant does not complete the entire survey, they will not be included in the analysis.

Exploratory analysis

No response

Other

Other

No response

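### The Hypothesis 2 verdict rests on 1000 bootstrap draws with no stated seed, so a borderline mediation result can change from run to run; more draws cut this about threefold.

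*Combined protocol and SAP*

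**What the plan says.** Under Analysis Plan, Statistical models, H2 is tested by a causal mediation analysis with the R mediation package. On precision the plan says only: "We will generate 95% confidence intervals by using 1000 bootstrap simulations". On the basis for the conclusion it says: "The unstandardized point estimate of the ACME and its 95% confidence intervals will be interpreted". A significant ACME is to be read as support for the proposed mechanism. For the other case the plan says: "If the ACME is non-significant, we will identify where the causal path breaks down".

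Under Inference criteria, the general rule is: "We will use the standard $p=0.05$ criteria for determining if the results are significantly different".

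The plan states no seed, no interval type (percentile or bias-corrected) and no rule for a result close to the boundary. The sample size rationale covers only the comparison of proportions between conditions: "A sample size of 61 per group was calculated to yield at least 90% power to detect a 30 percentage point difference between conditions". No power or precision figure is given for the mediation analysis.

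**The concern.** A bootstrap interval carries two kinds of error. One is sampling error, which only more participants can reduce. The other is Monte Carlo error from using a finite number of resamples, which the analyst can make as small as wanted. Here the limit that decides H2 is a 2.5% tail quantile estimated from 1000 draws, and a fixed cut-off is applied to it.

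Near that cut-off, two analysts who follow the plan exactly on the same data could report opposite verdicts on H2 and then follow different lines of interpretation. With no seed stated, a borderline result could also be rerun until it falls on the preferred side without departing from the written plan. A registered analysis should return one answer from one data set.

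**Working it through.** **Inputs from the plan.** 1000 draws, 95% interval, criterion 0.05, target of 122 participants (about 61 per condition).

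**Assumptions, not in the plan.** A percentile interval; a two-sided p equal to twice the smaller tail; 25 or fewer of 1000 draws beyond zero counted as significant; and, for the averaged figures, an approximately normal ACME estimate.

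**The plan's own figure.** The only stated precision figure belongs to H1. Exact power of the two-sided Fisher test for 35% vs 65% is 0.9007 at 61 per group and 0.892 at 60, so the stated 61 reproduces. There is no H2 figure to reproduce.

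**Step 1: Monte Carlo error for B draws.**
- Draws in the deciding tail: 0.025 × 1000 = 25.
- Standard error of the two-sided p near 0.05 = 2 × √(0.025 × 0.975 / B).
  - B = 1000: 0.0099, so 0.05 ± 1.96 × 0.0099 gives about 0.031 to 0.069.
  - B = 10,000: 0.0031, giving about 0.044 to 0.056.
- Standard error of a 95% limit, in units of the ACME's own standard error = √(0.025 × 0.975 / B) / φ(1.96), where φ is the standard normal density.
  - B = 1000: 0.084.
  - B = 10,000: 0.027.
- The ratio between the two is √10 = 3.16.

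**Step 2: stability of the verdict for a given data set.** Let p be the value that unlimited draws would give. The number of draws beyond zero is Binomial(B, p/2), and P(sig) is the chance that it is at most 0.025B. Two independent runs disagree with probability 2 × P(sig) × (1 − P(sig)).

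| p, unlimited draws | P(sig), 1000 | P(sig), 10,000 | Two runs disagree, 1000 | Two runs disagree, 10,000 |
|---|---|---|---|---|
| 0.04 | 0.890 | 0.9998 | 19.6% | 0.05% |
| 0.045 | 0.745 | 0.955 | 38.0% | 8.5% |
| 0.05 | 0.553 | 0.517 | 49.4% | 49.9% |
| 0.055 | 0.359 | 0.065 | 46.0% | 12.2% |
| 0.06 | 0.204 | 0.0015 | 32.5% | 0.3% |

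At p = 0.03 and p = 0.07, two 1000-draw runs disagree in 1.2% and 8.7% of cases.

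**Step 3: average over the data sets that could arise.** This weights the disagreement probability by a normal distribution for the estimate.

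| True ACME | Disagree, 1000 | Disagree, 10,000 |
|---|---|---|
| none | 1.1% | 0.35% |
| 1.96 SE (50% power) | 3.8% | 1.2% |
| 2.80 SE (80% power) | 2.6% | 0.8% |
| 3.24 SE (90% power) | 1.6% | 0.5% |

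**Step 4: check on an actual bootstrap.** One data set of 122 was simulated with a linear mediator model and a logistic outcome model. The coefficients were assumed, and the data set was chosen to be borderline. With 60,000 draws its p was 0.038. The lower limit was above zero in 93.6% of 1000-draw runs and in 100% of 10,000-draw runs. Computing time was about 0.17 seconds per 1000 draws and 1.7 seconds per 10,000 in Python; timing in R was not tested.

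**The case against.** The strongest reply is that 1000 draws is an explicit, prespecified choice and that the gain from more is small.

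- **Rarity.** The large disagreement rates apply only if p already lies near 0.05. Averaged over studies, the gain is at most 2 to 3 verdicts per 100 (3.8% down to 1.2%). This stands, and it limits the weight of the point.
- **Sampling error dominates.** Monte Carlo noise of 0.084 of a standard error adds only 0.084² ≈ 0.7% to the variance of a limit. This stands.
- **Little depends on it.** The primary analysis is the two-condition comparison, and the follow-up to a non-significant ACME is interpretive. H2 is also limited more by its mediator, which is rated after the choice and refers to the hospital already picked. This stands, but it does not justify avoidable noise in a registered test.
- **Interval and cut-off.** The plan does not name the interval type, and counting rules matter. If significance needs 24 rather than 25 draws or fewer, the wrong-verdict rates at p = 0.045 and 0.055 move from 25% and 36% to 32% and 29%. The size of the effect is similar.

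What fails is the claim that more draws are mere preference: they have no real downside and cut the seed-dependence of the verdict about threefold.

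Two stronger readings are tempting. A reader might infer that ten times more draws would remove the problem. It would not: at p = 0.045 and 0.055 the verdict is still wrong in 4.5% and 6.5% of runs with 10,000 draws, and at exactly 0.05 it is a coin toss at any number. A reader might also infer that the plan lets a rounded p-value decide H2. The text does not support this: Statistical models already bases interpretation on the ACME and its interval, and the Inference criteria section mentions no rounding.

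**Conclusion.** The point holds as a minor one. With 1000 draws and no stated seed, the H2 verdict can depend on the run when the p-value from unlimited draws lies between about 0.03 and 0.07. Over all studies this would produce opposite verdicts from two runs in about 1% to 4% of cases, against about 0.4% to 1.2% with 10,000 draws. These figures rest on the percentile interval and normal model assumed above. The binomial figures for a given p need the interval assumption but not the normal one. The documents do not support a wider claim: the plan's H1 test and its sample size do not use the bootstrap.

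**What to change.** In Statistical models, replace the 1000 simulations with: *at least 10,000 bootstrap resamples with a prespecified, reported seed*. The two parts do different jobs. The extra draws cut Monte Carlo error by a factor of 3.16, and the seed makes the reported run reproducible and closes the route of rerunning a borderline result, without reducing the error. Naming the interval type in the same sentence would settle what the draws are used for. No new statement that the interval decides H2 is needed.

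The cost is one edited sentence and probably seconds to minutes of computing. No participants are added.
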